2 OBJECTIVES AND ENDPOINTS

2.1 Primary Objective

• To assess the clinical efficacy of Auxora in patients with severe COVID-19 pneumonia

2.2 Secondary Objectives

- To assess the safety and tolerability of Auxora in patients with severe COVID-19 pneumonia
- To determine the pharmacokinetic profile of Auxora in patients with severe COVID-19 pneumonia

2.3 Endpoints

- Primary efficacy endpoint:
 - o Time to recovery
- Secondary efficacy endpoints:
 - o All-Cause Mortality at Day 60
 - o All-Cause Mortality at Day 30
 - Proportion of patients requiring invasive mechanical ventilation or dying during the
 60 days from the SFISD
 - Proportion of patients requiring invasive mechanical ventilation during the 60 days from the SFISD
 - o Difference in outcomes measured by the 8-point ordinal scale through Day 12
 - o Difference in outcomes measured by the 8-point ordinal scale through Day 30
 - Number of Days in the Hospital
 - Number of Days in the ICU
- Safety endpoints
 - The incidence of TEAEs and SAEs
 - The intensity and relationship of TEAEs and SAEs
 - o Clinically significant changes in vital signs and safety laboratory results

3 INVESTIGATIONAL PLAN

3.1 Study Design

Part 1 was a randomized open-label study that consisted of two arms. In one arm, 60 patients who were receiving low flow supplemental oxygen at Screening were to randomize 2:1 to Auxora or standard of care. In the other arm, 60 patients who were receiving high flow supplemental oxygen delivered using high flow nasal cannula at Screening were to randomize 2:1 to Auxora or standard of care. The independent safety committee conducted a review after the first 12 patients were dosed in the low-flow arm. The committee recommended continuing the trial unchanged until the next safety review committee meeting. After the initial independent safety committee review, the FDA asked for a limitation of further enrollment in the open-label study and for the study to transition to a blinded, placebo-controlled study. Both arms of Part 1 ceased further enrollment and follow-up of patients enrolled in Part 1 was to Day 30 only.

Part 2 is a randomized, double blind, placebo-controlled study in which initially up to 400 patients receiving supplemental oxygen at Screening, and who meet all of the inclusion criteria and none of the exclusion criteria, were to be randomized 1:1 to receive Auxora plus standard of care or Placebo plus standard of care. After a blinded analysis of the mechanical ventilation and death rate in the subgroup of patients with an imputed $PaO_2/FiO_2 > 200$ were randomized into the study, the number of patients in the subgroup was capped at 26. The study sample size remained 320 for patients with an imputed $PaO_2/FiO_2 \le 200$. When enrolling both subgroups, patients were stratified to ensure balanced randomization between the Auxora and Placebo arms.

The dose of Auxora will be 2.0 mg/kg (1.25 mL/kg) administered at 0 hour, and then 1.6 mg/kg (1 mL/kg) at 24 hours and 1.6 mg/kg (1 mL/kg) at 48 hours from the SFISD. The dose of Placebo will be 1.25 mL/kg administered at 0 hour and then 1 mL/kg at 24 hours and 1 mL/kg at 48 hours from the SFISD. The SFISD should occur within 12 hours of the patient or LAR providing informed consent. The dosing will be based on actual body weight obtained at the time of hospitalization or screening for the study. As described in the pharmacy manual, there will be an upper limit of the absolute dose (volume) of Auxora and volume of Placebo that will be administered for patients weighing more than 125kg.

A study physician or appropriately trained delegate will perform assessments at Screening, immediately prior to the SFISD, and immediately prior to each subsequent infusion. At 72 hours after the SFISD, the patient will be assessed every 24 hours (±4 hours) until 240 hours after the SFISD, then q48 hours until Day 30 after the SFISD, or until discharge if earlier. Patients who are discharged before Day 25 after the SFISD will be followed-up at Day 30 (±5 days) and Day 60 (±5 days) for a safety and mortality assessment.

After the first 50 patients were randomized in Part 2, an Independent Data Monitoring Committee (IDMC) evaluated safety data from the study and agreed with capping the number of patients with an imputed $PaO_2/FiO_2 > 200$ at 26 and to continue the study enrolling only patients with an imputed $PaO_2/FiO_2 < 200$. The IDMC will again review the safety data after the 70^{th} patient in the imputed $PaO_2/FiO_2 < 200$ subgroup completes the study and when the 200^{th} patient in the imputed $PaO_2/FiO_2 < 200$ subgroup is randomized into the study.

A sample size re-estimation procedure will be applied when the first 70 patients in the imputed $PaO_2/FiO_2 \le 200$ subgroup have completed or discontinued from the study. The IDMC will perform the procedure and will recommend to CalciMedica to increase or not increase the study sample size. No ongoing study patients will be included in this sample size re-estimation procedure. The sample size will be re-estimated to provide a conditional power of 90%, based on the evaluation of the treatment efficacy.

3.2 End of Study

The End of Study is considered the date on which the last patient randomized completes the visit on Day 60, unless CalciMedica terminates the study early.

3.3 Sponsor Termination of the Study

CalciMedica intends to complete the study as outlined. CalciMedica reserves the right, however, to terminate the study at any time because of:

- A directive from the FDA
- A lack of enrollment
- A recommendation from the IDMC

4 SELECTION OF PATIENTS

4.1 Inclusion Criteria

All of the following must be met for a patient to be randomized into the study:

- 1. Has laboratory-confirmed SARS-CoV-2 infection as determined by polymerase chain reaction (PCR) or other commercial or public health assay in any specimen, as documented by either of the following:
 - o PCR positive in sample collected < 72 hours prior to randomization; or
 - PCR positive in sample collected ≥ 72 hours prior to randomization, with inability to obtain a repeat sample (e.g. due to lack of testing supplies, or limited testing capacity, or results taking >24 hours, etc.) or progressive disease suggestive of ongoing SARS-CoV-2 infection;
- 2. At least 1 of the following symptoms:
 - Fever, cough, sore throat, malaise, headache, muscle pain, dyspnea at rest or with exertion, confusion, or respiratory distress;
- 3. At least 1 of the following signs at Screening or noted in the 24 hours before Screening:
 - o PaO₂/FiO₂ ≤200 when receiving supplemental oxygen. The PaO₂/FiO₂ may be estimated from pulse oximetry (Appendix 1) or determined by arterial blood gas;
 - o If SpO₂≥97%, receiving 10L or more of supplemental oxygen;
- 4. The presence of a respiratory infiltrate or abnormality consistent with pneumonia that is documented by either a CXR or CT scan of the lungs;
- 5. The patient is ≥ 18 years of age;
- 6. A female patient of childbearing potential must not attempt to become pregnant for 39 months, and if sexually active with a male partner, is willing to practice acceptable methods of birth control for 39 months after the last dose of study drug;
- 7. A male patient who is sexually active with a female partner of childbearing potential is willing to practice acceptable methods of birth control for 39 months after the last dose of study drug. A male patient must not donate sperm for 39 months;
- 8. The patient is willing and able to, or has a legal authorized representative (LAR) who is willing and able to, provide informed consent to participate, and to cooperate with all aspects of the protocol.

4.2 Exclusion Criteria

Patients with any of the following conditions or characteristics must be excluded from randomizing:

- 1. Expected survival or time to withdrawal of life-sustaining treatments expected to be <7 days;
- 2. Do Not Intubate order;

- 3. Home mechanical ventilation (noninvasive ventilation or via tracheotomy) except for continuous positive airway pressure or bi-level positive airway pressure (CPAP/BIPAP) used solely for sleep-disordered breathing;
- 4. PaO₂/FiO₂ ≤75 at the time of Screening. The PaO₂/FiO₂ may be estimated from pulse oximetry (Appendix 1) or determined by arterial blood gas;
- 5. Noninvasive positive pressure ventilation;
- 6. Invasive mechanical ventilation via endotracheal intubation or tracheostomy;
- 7. ECMO;
- 8. Shock defined by the use of vasopressors;
- 9. Multiple organ dysfunction or failure;
- 10. Positive Influenza A or B testing if tested as local standard of care;
- 11. The patient has a history of:
 - a. Organ or hematologic transplant;
 - b. HIV
 - c. Active hepatitis B, or hepatitis C infection;
- 12. Current treatment with:
 - a. Chemotherapy;
 - b. Immunosuppressive medications or immunotherapy (see Section 5.3 for list of prohibited immunosuppressive medications and immunotherapy) at the time of consent;
 - c. Hemodialysis or Peritoneal Dialysis;
- 13. Have a history of venous thromboembolism (VTE) (deep vein thrombosis [DVT] or pulmonary embolism [PE]) within 12 weeks prior to screening or have a history of recurrent (> 1) VTE;
- 14. The patient is known to be pregnant or is nursing:
- 15. Currently participating in another study of an investigational drug or therapeutic medical device at the time of consent;
- 16. Allergy to eggs or any of the excipients in Auxora.

4.3 Re-Screening

A patient who fails the initial screening because either the clinical symptoms or signs noted in inclusion criteria 2 or 3 were not present may be rescreened twice again within 48 hours of the original screening.

5 TREATMENT OF PATIENTS

5.1 Overview

All patients enrolled in the study should receive care consistent with local standard of care. Patients with worsening respiratory failure should receive conservative intravenous fluid strategies such as FACTT LITE. All patients should receive pharmacological prophylaxis to prevent the development of venous thromboembolic disease. The type and dose of prophylaxis should be determined by local standard of care.

Patients enrolled in the study should receive dexamethasone, or equivalent dose of another corticosteroid, as standard of care. If patients are not receiving dexamethasone at the time of randomization into CARDEA, starting dexamethasone during the hospitalization should be considered. If the patient is already receiving dexamethasone at the time of randomization, dexamethasone should be continued on its established dosing schedule. The COVID-19 Treatment Guidelines Panel of the National Institutes of Health recommends using dexamethasone (at a dose of 6 mg per day, given orally or intravenously, for up to 10 days) in patients with COVID-19 who require supplemental oxygen. Before initiating dexamethasone, the potential risks and benefits of administering corticosteroids should be assessed including risks for hyperglycemia and secondary infections. At this time, it is not known whether other corticosteroids, such as prednisone, methylprednisolone, or hydrocortisone, will have a similar benefit to dexamethasone. Of note, the dose equivalencies for dexamethasone 6 mg daily are prednisone 40 mg, methylprednisolone 32 mg, and hydrocortisone 160 mg.

If patients are not receiving remdesivir at the time of randomization into CARDEA, starting remdesivir during the hospitalization may be considered. If the patient is already receiving remdesivir at the time of randomization, remdesivir should be continued on its established dosing schedule. The suggested dose of remdesivir for adults weighing ≥40 kg and not requiring invasive mechanical ventilation and/or ECMO is a single dose of 200 mg infused intravenously over 30 to 120 minutes on Day 1 followed by once-daily maintenance doses of 100 mg infused intravenously over 30 to 120 minutes for 4 days (days 2 through 5). If a patient does not demonstrate clinical improvement, treatment may be extended for up to 5 additional days (i.e., up to a total of 10 days). Auxora and remdesivir should not infuse at the same time but should be given sequentially in any order.

Patients may also be considered for the administration of convalescent plasma in the study as per local standard of care.

Immunosuppressive medications or immunotherapies are prohibited in patients randomized into the study (Section 5.3 for list of prohibited medications). The use of dextromethorphan is discouraged in patients randomized into the study.

5.2 Discharge Criteria

Patients should remain in the hospital until all 3 doses of study drug have been administered.

If the patient is ready to be discharged before all doses of study drug have been administered, the PI or treating physician should contact the Medical Monitor prior to discharging the patient.

5.3 Prohibited Medications

Any medication, with the exception of those listed below, may be given at the discretion of the PI. Medications that should not be administered during the study to patients randomized in the study include:

- Chemotherapy
- Cyclosporine, Tacrolimus
- Sirolimus, Everolimus
- Azathioprine
- Cyclosphosphamide
- Methotrexate
- Mycophenolate
- Leflunomide
- Biologics/Monoclonals: abatacept, adalimumab, alemtuzumab, anakinra, basilizimab, belimumab, bevacizumab, brodalumab, canakinumab, certolizumab, cetuximab, clazakizumab, daclizumab, eculizumab, etanercept, golimumab, infliximab, interferon, ixekizumab, muromonab, natalizumab, omalizumab, rituximab, sarilumab, secukinumab, tocilizumab, trastuzumab, ustekinumab, vedolizumab
- Baricitinib
- Tofacitinib

Note further use of Dextromethorphan is discouraged.

5.4 Compliance

Only the PI or his/her appropriately trained study staff will administer study drug to patients randomized in the trial in accordance with the protocol. Study drug must not be used for any reasons other than that described in the protocol.

6 PROCEDURES

6.1 Enrollment Procedures

Patients will be randomized 1:1 to Auxora plus local standard of care versus Placebo plus local standard of care.

6.2 Discontinuation and Withdrawal

The term discontinuation refers to a patient or PI discontinuing the administration of study drug before all 3 doses are administered despite the patient remaining in the hospital. Patients who do not receive all 3 doses because the treating physician discharged them from the hospital will not be considered to have discontinued study medication.

Patients have the right to discontinue the administration of study drug at any time for any reason, without prejudice to their medical care. The PI may discontinue the administration of study drug because of an adverse event or change in medical status that raises a safety concern about the patient receiving additional doses of study drug. The PI **must** discontinue the administration of study drug if the patient is diagnosed with a new or recurrent malignancy, or if the patient was concomitantly administered a prohibited medication. If possible, the PI should contact the Medical Monitor to review the reasons for a patient's discontinuation from study drug. The PI should also record the reason for the discontinuation in the eCRF and appropriate source documents at the site. Even if the patient discontinues receiving study drug, diligence should occur to ensure that all study visits and assessments are completed.

Withdrawal refers only to the complete withdrawal of the patient from the study because of the withdrawal of consent. The PI should inform the Medical Monitor of the withdrawal of consent and record the withdrawal of consent in the eCRF and appropriate source documents at the site.

Patients who ask for a new DNI order after randomization into the study should be discontinued from the study and no further assessments will be performed other than the mortality assessment at Days 60 and 30.

7 STUDY DRUG MATERIALS AND MANAGEMENT

7.1 Auxora Product Description

Auxora is to be administered as an IV infusion and is supplied as a translucent, white to yellowish, sterile, non-pyrogenic emulsion containing 1.6 mg/mL of the active pharmaceutical ingredient CM4620. Auxora is supplied as an 80 mL fill in a 100 mL single-use glass vial. Auxora contains egg phospholipids, medium chain triglycerides, glycerin, edetate disodium salt dehydrate (EDTA), sodium hydroxide (as needed to adjust pH), and sterile water for injection (Table 4).

Table 4. Auxora Product Information

Product Name:	CM4620 Injectable Emulsion	
Dosage Form:	Injectable Emulsion (Liquid)	
Concentration of CM4620	1.6 mg/mL	
Route of Administration	IV	
Physical Description	Translucent, non-separated, white to yellowish emulsion	
Inactive Ingredients	Sterile Water for Injection USP, Egg Phospholipid NF (80% Phosphatidylcholine), Medium Chain Triglycerides NF, Glycerin USP, and Edetate Disodium Salt Dihydrate (EDTA) USP. Sodium Hydroxide and Hydrochloric Acid may be added to adjust the pH.	
Manufacturer	Bioserv Corporation San Diego, CA 92121	

7.2 Placebo Product Description

Matching Placebo is to be administered as an IV infusion and is supplied as a translucent, white to yellowish, sterile, non-pyrogenic emulsion carrier containing no active pharmaceutical ingredient. Placebo is supplied as an 80 mL fill in a 100 mL single-use vial. Placebo contains the same ingredients as Auxora except that it does not contain CM4620.

7.3 Auxora and Placebo Storage

Auxora and Placebo must be maintained in a secure location with refrigerated temperature conditions of 2 to 8°C (36 to 46°F). Precaution should be taken to ensure that the Auxora and Placebo do not freeze. Temperature logs should be maintained and available during monitor review. When a temperature is noted outside the range of 2°C to 8°C lasting for 24 hours or more, or if the temperature exceeds 20°C (68°F), or is below 0°C (32°F), CalciMedica or its designee must be notified as soon as possible. The stability of Auxora and Placebo has been demonstrated to 24 months and is being evaluated for longer periods in ongoing studies.

7.4 Auxora and Placebo Preparation

The study pharmacist and/or designee will be responsible for the preparation and dispensation of Auxora and Placebo. Prior to administration, Auxora and Placebo both must be transferred to a sterile container a using sterile technique. Specific details on how to prepare Auxora and Placebo, as well as the specific components that will be used to administer both Auxora and

Placebo, will be provided in the Pharmacy Manual. The Pharmacy Manual will also contain tables detailing the selected dose level and volume of administration of Auxora and Placebo.

7.5 Auxora and Placebo Administration

Both Auxora and Placebo will be administered intravenously over 4 hours at a constant rate of infusion. They will be administered every 24 hours (±1 hours) for three consecutive days for a total of 3 doses. The dose and volume of Auxora, and the volume of Placebo, that will be administered will be calculated using the patient weight obtained at the time of hospitalization or during screening. A line into a peripheral or central vein may be used for the infusion. The peripheral IV should be 20 gauge in size or larger. The peripheral IV or central line port should be dedicated when administering Auxora or Placebo other than 0.9% normal saline. Auxora and Placebo are compatible with 0.9% normal saline. The IV tubing used to administer Auxora and Placebo must contain a 1.2 micron filter. The Pharmacy Manual will contain a recommended procedure to prime the IV tubing and flush the tubing, but this may be adapted to local nursing standards. 0.9% normal saline may be used to clear the line to ensure that the volume to be infused (VTBI) is completely administered. If the administration of Auxora or Placebo is stopped because of a technical reason, such as failure of the IV site, or IV pump malfunction, the administration of Auxora or Placebo should be resumed when the technical reason is resolved, and continued at the same rate until the infusion is completed. The total amount of time for the start of infusion to end of infusion of Auxora or Placebo should be recorded.

CalciMedica may modify at any time the administered doses of Auxora or volumes of Placebo, the days of infusion, the timing of the infusion and the rate of infusion based on review of the safety and tolerability data by the IDMC. If the administration of Auxora or Placebo is stopped because of a serious adverse event that is considered to be probably or definitely related to Auxora or Placebo, the Medical Monitor must be immediately contacted.

Although the administration of the infusion should be set up to be completed over four hours, it is expected that there will be minor variability based on the equipment used and calibration of the equipment. The acceptable infusion timeframe is 4 hours (+/- 30 minutes).

7.6 Packaging and Labeling

Preparation, packaging and labeling of Auxora and Placebo will be in accordance with current Good Manufacturing Practice of Medicinal Products (GMP) guidelines. Medication labels will comply with legal requirements for labeling of investigational products in the United States and the UK.

7.7 Accountability, Handling and Disposal

The PI or designee will ensure that deliveries of Auxora and Placebo from CalciMedica or its designee are received by a responsible person, and such deliveries are recorded; that Auxora and Placebo are handled and stored safely and properly; that Auxora and Placebo are only dispensed to study patients in accordance with the protocol; and that unused Auxora and Placebo is returned to CalciMedica or its designee or disposed of using standard procedures approved of in advance by CalciMedica or its designee. Appropriately trained study staff will administer all doses of Auxora and Placebo. The pharmacy will maintain a record of Auxora and Placebo accountability.

8 VISITS AND STUDY SPECIFIC ASSESSMENTS

8.1 Screening

The PI or designee must provide informed consent to the patient, or LAR, allowing the patient or LAR adequate time to consider, ask questions and receive answers, prior to agreeing to participate.

• Record the time of the patient or LAR provides informed consent

After informed consent is obtained, the following procedures are to be performed:

- Record Vital Signs
- Record Weight: may use weight obtained as part of standard of care
- Record results of Influenza A, B and Respiratory Panel if performed as local standard of care
- Record results of Sars-CoV-2 testing
- Record results of CXR or CT scan documenting a pulmonary infiltrate
- Record the lowest SpO₂ in the previous 24 hours and the time it was performed. The FiO₂ at the time of the SpO₂ measurement will also be recorded
- Record the SpO₂ and FiO₂ at the time closest to the Screening assessment
- Complete and record results of pregnancy test for women of child-bearing potential
- Record ABG and time drawn if performed as part of standard of care
- Complete Daily Assessment Ordinal Scale

If the patient satisfies all of the inclusion criteria and none of the exclusion criteria, proceed to baseline assessment.

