8.13.4 SpO_2/FiO_2

The SpO₂ will be determined using a hospital approved pulse oximeter. The PI or appropriately trained study coordinator should review the pulse oximetry waveform determining the SpO₂ to attest to its adequacy. The FiO₂ at the time of the SpO₂ measurement will be recorded. For patients with assisted breathing, the FiO₂ is read from the controlled oxygen source e.g. Venturi masks, ventilator and CPAP/BIPAP systems with calibrated oxygen blenders. For patients breathing unassisted i.e. room air, the FiO₂ is recorded as 0.21. If a patient is on an uncontrolled oxygen source, the following table provides the estimated FiO₂:

Table 5. Conversion of O₂ Flow to FiO₂

Supplemental Oxygen L/min	Estimated FiO ₂ (%)								
	Nasal Cannula	Face Mask	Face Mask with Reservoir						
Room Air	21								
1	24								
2	28								
3	32								
4	36								
5	40	40							
6	44	50	60						
7		50	70						
8		60	80						
9		60	90						
10		60	95						

Adapted from Vincent et al., 2009

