10.8.10 Subgroup and Exploratory Analyses

Subgroup analyses will be performed to explore how time to recovery is influenced by baseline variables and to evaluate the treatment effect at different levels of each of these variables. The Kaplan-Meier analysis and Cox model will be performed by subgroup levels of the baseline variables listed below:

- Age $(<75, \ge 75)$
- Baseline PaO_2/FiO_2 (>200, ≤100, 101-200, 201-300, all randomized patients)
- Receiving high flow oxygenation versus low flow oxygenation at randomization
- Race (White, Black, Asian, Other).
- Gender (Male, Female)
- BMI ($<30, \ge 30$)
- Remdesivir (being already administered at randomization, administration started after randomization, never administered)
- Dexamethasone (being already administered at randomization, administration started after randomization, never administered)
- Remdesivir and Dexamethasone (being already administered together at randomization or administered together starting after randomization)
- Convalescent plasma (being administered at randomization, administration started after randomization, never administered)

Additional subgroups may also be further described in the Statistical Analysis Plan.

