8.3 Demographic, Other Baseline Characteristics and Medication

8.3.1 Demographic and Baseline Characteristic

Patient demographic and baseline characteristics will be summarized by mean, SD, median, minimum, and maximum for continuous variables; and by counts and percentages for categorical variables. Summaries will be provided separately for each treatment group and then total subjects. The following subject demographic and baseline characteristic are summarized. The demographic variables consist of age, age category (18-39, 40-64, 65+), sex, ethnicity and race. Baseline characteristics include height, weight, body mass index (BMI), time from symptom onset to randomization in days, baseline scores on 8-point ordinal scale, baseline imputed PaO₂/FiO₂ and category (≤ 200 , ≥ 201), baseline d-dimer, baseline ferritin, and baseline CRP. Efficacy and Safety Analysis Sets will be used for the summaries.

Other baseline variables such as relevant medical history or other medically relevant criteria could also be included in the baseline tables.

The 8-point ordinal scale is defined as:

Scale	Description
1	Death
2	Hospitalized, requiring invasive mechanical ventilation or ECMO
3	Hospitalized, requiring noninvasive mechanical ventilation or high flow supplemental oxygen
4	Hospitalized, requiring low flow supplemental oxygen
5	Hospitalized, not requiring supplemental oxygen but requiring ongoing medical care
6	Hospitalized, not requiring supplemental oxygen or ongoing medical care
7	Discharged, requiring supplemental oxygen
8	Discharged, not requiring supplemental oxygen

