8.5.5 Supportive Secondary Efficacy Analysis

8.5.5.1 All-cause mortality at Day 30 visit

The analysis will be the same as the Day 60 visit analysis.

8.5.5.2 Proportion of patients requiring invasive mechanical ventilation or dying during the 60 days from the SFISD

Time to requiring invasive mechanical ventilation is defined as time from SFISD to the first time the patient requiring invasive mechanical ventilation or dying. Proportion of patients requiring invasive mechanical ventilation or dying is defined as the proportion at study Day 60. Day 60 rate for each treatment group will be estimated by the Kaplan-Meier procedure. Hypothesis testing will be based on the Kaplan-Meier estimates and standard errors estimated by Greenwood formula using the log-log transformation of the survival function stratified by the baseline imputed $\text{PaO}_2/\text{FiO}_2$ of ≤ 100 vs. >100 . Subjects who do not have death or require invasive mechanical ventilation in the record will be censored on the last known status date (administrative censoring). Patients who recovered, were discharged, had 30 day follow up where they remained recovered, and did not use invasive mechanical ventilation during the study, will be censored at Day 65 as being alive/recovered without event if data is missing.

8.5.5.3 Proportion of patients requiring invasive mechanical ventilation during the 60 days from the SFISD

The analysis will be the same as the proportion of patients requiring invasive mechanical ventilation or dying during the 60 days from the SFISD. Subjects who have death and do not require invasive mechanical ventilation will be censored on the date of death (hypothetical strategy). Patients who recovered, were discharged, had 30 day follow up where they remained recovered, and did not use invasive mechanical ventilation during the study, will be censored at Day 65 as being alive/recovered without event if data is missing.

8.5.5.4 Differences in Outcomes Measured by an 8-Point Ordinal Scale at Day 12

Proportion of patients in each category of 8-point ordinal scale at Day 12 will be calculated for each treatment group, and the odds ratio will be estimated. The proportion will be compared between the 2 treatment groups using a proportional odds model with fixed factor of treatment groups.

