8.8.2 Subgroup Analyses

Subgroup analyses will be performed to explore how time to recovery through Day 60 visit and mortality at Day 60 visit are influenced by baseline variables and to evaluate the treatment effect at different levels of each of these variables. The Kaplan-Meier analysis, Cox model and CMH test will be performed by subgroup levels of the baseline variables listed below:

- Age ($<65, \geq65$)
- Baseline CRF calculated imputed $\text{PaO}_2/\text{FiO}_2$ ($\leq100, 101-200, \geq201$)

- Race (White, Black, Asian, Other).
- Gender (Male, Female)
- BMI ($<30, \geq 30$)
- Remdesivir (being already administered at randomization, administration started after randomization, never administered)
- Dexamethasone (being already administered at randomization, administration started after randomization, never administered)
- Remdesivir and Dexamethasone (being already administered together at randomization or administered together starting after randomization)
- Convalescent plasma (being administered at randomization, administration started after randomization, never administered)

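### The SAP omits the protocol's high-flow versus low-flow subgroup without explanation, and the Day 12 and Day 30 ordinal models leave out the Screening category of the same scale

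*Protocol*

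**What the plan says.** **Collection.** Protocol 8.1 lists "Complete Daily Assessment Ordinal Scale" among the Screening procedures. Section 8.4 does not repeat it at 0 hour; the next score is at 24 hours. Under the baseline rule in SAP 8.1.4.1, the Screening score is therefore the baseline value.

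**Subgroup.** Protocol 10.8.10 lists "Receiving high flow oxygenation versus low flow oxygenation at randomization" among ten subgroup factors for time to recovery. It adds: "Additional subgroups may also be further described in the Statistical Analysis Plan". SAP 8.8.2 extends the subgroup work to Day 60 mortality and states: "The Kaplan-Meier analysis, Cox model and CMH test will be performed by subgroup levels of the baseline variables listed below". Its list has nine factors, and oxygen support is not one of them.

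**Use of the baseline score.** In the SAP, "baseline scores on 8-point ordinal scale" appear in the descriptive summary of 8.3.1 and in no model. The Day 12 comparison (SAP 8.5.5.4) is made "using a proportional odds model with fixed factor of treatment groups", and Day 30 (8.5.5.5) follows it. Protocol 10.8.6 and 10.8.7 specify the same treatment-only model.

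**Contrast.** The MMRM analyses of PaO2/FiO2 (SAP 8.6.1) and biomarkers (SAP 8.8.1) do include the baseline value of the endpoint.

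**The concern.** High and low flow are separate rungs (3 and 4) of the scale that defines recovery, and Part 1 was divided on this factor: "In the other arm, 60 patients who were receiving high flow supplemental oxygen delivered using high flow nasal cannula at Screening" (Protocol 3.1). The protocol says whether the effect on recovery differs by oxygen support will be examined. The SAP, which states that it is based on protocol version 8.1, does not provide for that, and a reader cannot tell oversight from decision. If the analysis is run later, it may look post hoc although the protocol named it in advance.

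The ordinal models raise a second, independent issue. Patients start from two different rungs of the outcome scale, the starting rung is known for each of them, and the models ignore it. If the rung is prognostic, the comparison gives up power that the collected data could supply.

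**Working it through.** **1. The two subgroup lists.** The protocol has age, PaO2/FiO2, oxygen flow, race, gender, BMI, remdesivir, dexamethasone, both drugs together, and convalescent plasma. The SAP has all of these except oxygen flow. Some cut-points differ (age 75 in the protocol, 65 in the SAP), but no other factor is missing.

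**2. What the Screening score can be.** Noninvasive ventilation, invasive ventilation and ECMO are exclusions (Protocol 4.2), and Part 2 patients are on supplemental oxygen at Screening (3.1). That leaves essentially categories 3 and 4.

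**3. Does PaO2/FiO2 stand in for it?** Only partly.
- Protocol 8.13.4 reads FiO2 from the device on controlled sources. Otherwise: "If a patient is on an uncontrolled oxygen source, the following table provides the estimated" FiO2 (Table 5).
- A simple face mask at 8 L/min is assigned 0.60. At SpO2 95%, Appendix 1 gives 126, the same as for a device-read 0.60.
- Nasal cannula at 6 L/min (0.44) with SpO2 92% gives 145; FiO2 0.50 with SpO2 94% gives 142. Different support can share the 101-200 band.
- The timing differs as well. Baseline imputed PaO2/FiO2 is the worst value in the 24 hours before screening (SAP 8.1.4.1), whereas the protocol subgroup is support at randomization.

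**4. The plan's own event counts.** Schoenfeld's formula is d = 4(z₀.₉₇₅ + z₀.₉₀)² / (ln RR)², with z values 1.96 and 1.2816.
- RR 1.43: 4 × 3.2416² / 0.3577² gives 329, against 330 stated.
- RR 1.49: 4 × 3.2416² / 0.3988² gives 265, against 266 in SAP Table 4 for 320 patients.

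Both reproduce, so the sample size is not in question.

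**5. What a restored subgroup could show.** The documents give no high-flow share. I assume 30%, 50% or 70%, with the 266 events split in proportion and RR 1.49. Power is Φ(√d/2 × ln RR − 1.96), and the 95% CI factor is exp(1.96 × 2/√d).

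| High-flow share | Events | Power | CI: estimate ×/÷ |
|---|---|---|---|
| 30% | 80 | 43% | 1.55 |
| 50% | 133 | 63% | 1.40 |
| 70% | 186 | 78% | 1.33 |

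For the interaction, the ratio of the two RRs detectable with 80% power is exp(2.8016 × √(4/d₁ + 4/d₂)). This is 1.99 at an even split and 2.12 at 30/70.

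**6. The ordinal model with and without the Screening category.** Assumptions, none from the documents: treatment odds ratio 1.8; high-flow share 30-70%; reference Day 30 distribution, category 1 to 8, of 20, 6, 5, 3, 2, 1, 20 and 43%. With 320 patients and 700 to 1,500 simulated trials per scenario:

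| Baseline-category OR | Power, treatment only | Power, adjusted | Gain (points) |
|---|---|---|---|
| 2 | 78-79% | 80-81% | 1-2 |
| 4 | 71-77% | 78-81% | 4-7 |

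With no treatment effect, rejection rates were 4.1-6.5% unadjusted and 4.4-6.4% adjusted, with no systematic difference.

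**7. Where the gain comes from.** I solved the same model for expected counts at a 50% share and baseline odds ratio 4. The treatment-only model gives an odds ratio of 1.70 with standard error 0.2105 on the log scale, so z = 0.5306/0.2105 = 2.52. The adjusted model gives 1.80 with 0.2170, so z = 0.5878/0.2170 = 2.71. Power is Φ(2.52 − 1.96) = 71% against Φ(2.71 − 1.96) = 77%. The estimate moves away from 1 while the interval becomes about 3% wider (0.2170/0.2105). Under another assumed distribution the standard error went from about 0.203 to 0.203-0.207.

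**The case against.** **The SAP still covers oxygen need.** It keeps PaO2/FiO2 ≤100 versus 101-200 as a subgroup and stratifies the primary and mortality tests on it. By Appendix 1, a ratio ≤100 at SpO2 of 91% or more needs FiO2 above 0.60. Table 5 gives at most 0.44 by nasal cannula and 0.60 by simple face mask, so the lower band already captures much of the heavier support. This stands. A reader might infer that all information on effect by oxygen support is lost; the documents do not support that.

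**The treatment-only ordinal model is the protocol's own.** True: the SAP repeats it and did not create the weakness. These endpoints are supportive and lie outside the two tests under alpha control.

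**Adjustment does not improve precision.** Also correct. A reader might infer that the unadjusted interval is needlessly wide, but step 7 shows the reverse. Adjustment also changes the target from a marginal to a conditional odds ratio, which should be acknowledged.

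**The Screening score is not exactly support at randomization.** The first infusion may follow consent by up to 12 hours, and high flow is not defined for the scale in Part 2. This stands as a limitation. The Screening score is still the last ordinal value before randomization.

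**The change log proves nothing.** A reader might take its silence as an undisclosed removal. The log covers only changes from the previous SAP version, so it cannot show that.

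**Conclusion.** The point holds in two limited parts. First, the protocol and SAP disagree: a subgroup named in Protocol 10.8.10 is absent from SAP 8.8.2 with no reason given, and the retained PaO2/FiO2 subgroup replaces it only in part. The protocol promises it for time to recovery; Day 60 mortality would follow from the SAP's own extension. At the assumed shares the high-flow subgroup has 43-78% power and only about a two-fold interaction is detectable, so the result would be estimation and not a firm test.

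Second, the Day 12 and Day 30 models leave out a baseline value that is already collected. The cost is about 1 to 7 points of power, entirely dependent on the assumed treatment effect, outcome distribution, high-flow share and prognostic strength of the category.

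A reader might infer that the ordinal comparisons are invalid. They are not: type I error is about the same with or without the covariate. The primary and key secondary tests are unaffected. The change is worth making but is not critical.

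**What to change.** The two changes are independent.

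1. In SAP 8.8.2, restore high flow versus low flow for time to recovery and Day 60 mortality. Define it as Screening ordinal category 3 versus 4, the last ordinal value before randomization, and state how high flow was coded. Report estimates and the interaction with 95% confidence intervals. If the omission was deliberate, record the reason instead.

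2. In SAP 8.5.5.4 and 8.5.5.5, add the Screening ordinal category as a fixed factor. State that the odds ratio is then conditional on baseline category, and keep the treatment-only model as a sensitivity analysis.

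The cost is SAP wording and a few output rows; no new data are needed. The downsides are one more exploratory subgroup and a conditional rather than marginal odds ratio. Both changes should be fixed before the treatment codes are opened for the final analysis.
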